## 1.0 TRIAL SUMMARY

Abbreviated Title	A Multicenter, Open-label, Phase 2 Study of Imprime PGG and Pembrolizumab in Subjects With Advanced Melanoma Failing Front-line Treatment with Checkpoint Inhibitors (CPI) or Triple Negative Breast Cancer (TNBC) Failing Front-line Chemotherapy for Metastatic Disease
Trial Phase	2
Clinical Indication	Advanced Melanoma and Triple Negative Breast Cancer
Trial Type	Multicenter, Simon's 2-stage optimal design of Imprime PGG and pembrolizumab
Type of control	Historical control
Route of administration	Intravenous for both products
Trial Blinding	None
Treatment Groups	All subjects to receive Imprime PGG + pembrolizumab
Number of trial subjects	Up to N=94 in total (up to 41 with advanced melanoma, up to 53 with TNBC)
Estimated duration of trial	Approximately 3 years
Duration of Participation	Approximately 2 years for any individual subject

## 2.0 TRIAL DESIGN

[figure not shown]
### 2.1 Trial Design

The study will incorporate Simon's optimal 2-stage design with sample size fixed at 12 subjects each in Stage 1 for advanced melanoma and for Triple Negative Breast Cancer (TNBC) subjects. The safety criterion of  $\leq 4$  (or  $\leq 33\%$ ) subjects with Grade 3/4 adverse events in Cycle 1 within either tumor type must be met in order to proceed to Stage 2. The starting dose is 4 mg/kg for Imprime PGG. In the event there are a total of  $> 4$  (or  $> 33\%$ ) of subjects with Grade 3/4 adverse events in Cycle 1, the dose of Imprime PGG will be reduced to 2 mg/kg, and Stage 1 will be repeated at a dose of 2 mg/kg with an additional cohort of n=12 subjects. For the dose that meets the safety criterion in Stage 1, at least 1 response in melanoma subjects and 1 response in TNBC subjects amongst the 12 subjects within each tumor type must be observed in order to proceed to Stage 2.

Stage 2 will enroll an additional 17 subjects with melanoma, and 29 subjects with TNBC. For the dose that meets the Stage 1 safety criterion, success will be declared if at least 4 amongst the total of up to 29 subjects with melanoma, and 5 amongst the total of up to 41 subjects with TNBC achieve an objective response.

The study population will be those having failed front-line therapy, defined as any treatment regimen or regimens used specifically in the treatment of metastatic disease. Refer to [Section 5.1 on Entry Criteria](#) for the study-specific requirements.

## 2.2 Trial Diagram

\* ≤ 4 subjects or 33% of Stage 1 subjects does not include infusion reactions (from either study drug) which were subsequently controlled and reduced in Cycle 1 via ameliorating actions, and which did not recur in Cycle 2

### **3.0 OBJECTIVES AND HYPOTHESIS**

RECIST v1.1 criteria will be used for all applicable primary and secondary endpoints.

Immune related response criteria (irRECIST) will be used for exploratory efficacy endpoints.

#### **3.1 Primary Objectives and Hypothesis**

- **Objective:** To determine the Overall Response Rate (ORR) to Imprime PGG + pembrolizumab in subjects with advanced melanoma or metastatic TNBC
- **Safety:** To characterize the safety of Imprime PGG + pembrolizumab given in combination

**Hypothesis:** Restore (for melanoma) or enhance (for TNBC) sensitivity to checkpoint inhibitors (CPI) by appropriate and effective stimulation of the subject's innate and adaptive immune systems in those subjects who have failed front-line therapy

##### **Melanoma Subjects:**

- $H_0$ : ORR  $\leq 5\%$
- $H_A$ : ORR  $\geq 23\%$

##### **TNBC Subjects:**

- $H_0$ : ORR  $\leq 5\%$
- $H_A$ : ORR  $\geq 21\%$

Rejection of the null hypothesis will require documenting at least 4 objective responses among the total of up to 29 subjects with melanoma (Stage 1 + Stage 2), and 5 objective responses among the total of up to 41 subjects with TNBC (Stage 1 + Stage 2).

#### **3.2 Secondary Objectives**

##### **Objectives:**

- To determine the time to response (TTR), complete response rate (CRR), and duration of overall response (DoR) in subjects with advanced melanoma or metastatic TNBC when treated with Imprime PGG in combination with pembrolizumab
- To measure the Progression-Free Survival (PFS) and PFS rate at 6 months and 1 year in subjects with advanced melanoma or metastatic TNBC when treated with Imprime PGG in combination with pembrolizumab
- To measure overall survival (OS) and OS rate at 1 year in subjects with advanced melanoma or metastatic TNBC when treated with Imprime PGG in combination with pembrolizumab

- To profile pharmacokinetic (PK) data in subjects with advanced melanoma or metastatic TNBC when treated with Imprime PGG in combination with pembrolizumab

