tumor progression. The median TTP was 2.7 months (range: 1.2-16.2 months). In total, 18 (100.0%) subjects had recurrence, progression, or death. The median PFS was 2.2 months (range: 1.2-16.2 months). In total, 16 (88.9%) subjects died. The median OS was 6.6 months (range: 1.9-23.1 months). These data compare favorably with historical responses of cetuximab monotherapy in KRAS mutated subjects where ORR, DCR, and median OS have been reported to be 0%-1%, 10%-30%, and 19-21 weeks, respectively. Complete safety and efficacy results are reported in Section 5 of the Imprime PGG Investigators Brochure.

- Study BT-CL-PGG-LCA0822 [LCA0822] assessed 4 mg/kg Imprime PGG in combination with cetuximab and a standard regimen of carboplatin and paclitaxel therapy in first-line treatment of late stage (Stage IIIB or IV) NSCLC. The primary endpoint was ORR; secondary endpoints included DCR, OS, tumor response rates (CR, PR, and SD), DoR, TTP, safety of regimen, and PK profile. A total of 90 subjects were enrolled. Of these, 59/60 subjects randomized into the Imprime PGG arm received this treatment (1/60 received no study treatment). Thirty (30) subjects were randomized into the control arm and of these, 29/30 received treatment (1/30 received no study treatment). This study was closed on 04 November 2015 with final results available in November 2015. The addition of Imprime PGG (4mg/kg intravenous infusion) to weekly infusions of cetuximab in combination with carboplatin and paclitaxel chemotherapy administered Q3W in subjects with advanced NSCLC resulted in improved ORR, the primary endpoint of the study (36.6% in the Imprime PGG arm vs. 23.1% in the Control arm [ $p=0.2895$ ] based on central and 47.8% vs. 23.1% [ $p=0.0468$ ], respectively, based on investigator assessment). Of the secondary endpoints, results were (Imprime PGG vs. Control): median DoR of 4.4 vs. 4.1 months by central review and 3.8 vs. 4.7 months by investigator assessment; median TTP of 6.4 months vs. 6.0 months ( $p=0.6044$ ) by central review and 4.3 vs. 4.4 months ( $p=0.7305$ ) by investigator assessment; median OS of 11.7 months vs. 12.4 months ( $p=0.8972$ ). All available efficacy and safety results are reported in Section 5 of the Imprime PGG Investigators Brochure.

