### **5.8 Subject Withdrawal/Discontinuation Criteria**

#### **5.8.1 Withdrawal/Discontinuation Criteria**

Subjects will be encouraged to complete the study; however, they may voluntarily withdraw at any time without prejudice to future care. The Investigator will provide a written report describing the reason for discontinuation. If a subject discontinues study drug, every effort should be made to complete the assessments scheduled to occur during the Post-Treatment Visit and survival follow-up period. The subject will continue to be followed until completion of the study.

A subject may discontinue study drug for the following medical or administrative reasons:

- Adverse event: If a subject suffers an AE that in the judgment of the Investigator, presents an unacceptable consequence or risk to the subject, the subject may be discontinued from study drug
- Progressive Disease per irRECIST (see [Section 7.3.2](#))
- Subject decision: A subject may voluntarily discontinue from study drug at any time
- Intercurrent illness: A subject may discontinue study drug if, in the judgment of the Investigator, the subject develops an intercurrent illness or complication that is not consistent with the protocol requirements or that, in any way, justifies withdrawal from the study drugs, or that requires treatment with a restricted medication.
- Ineligibility to protocol entry criteria determined
- Lost to follow-up
- Administrative discontinuation: After consultation between the Investigator, the medical monitor, or the Sponsor when appropriate, a subject may be discontinued from study drug for the following administrative reasons:
  - Noncompliance (all occurrences of noncompliance must be documented on the appropriate eCRFs)

- Failure to receive study drug per protocol as defined in [Section 5.2 Trial Treatments](#)
- Failure to comply with protocol requirements
- Refusal of study drug administration (with reason documented)

In all cases, when subjects discontinue study drug, reasonable efforts should be made to monitor the subject for AEs and to complete follow-up assessments following such discontinuation. These efforts should be documented on the appropriate eCRF. The subject will continue to be followed for survival for the duration of the study.

If a subject withdraws consent for follow-up of survival, this must be documented, and no further efforts at contact will be attempted.

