### **9.1.3 Efficacy Analyses**

Efficacy analysis will be conducted separately for each tumor type. The primary efficacy endpoint is ORR, and the secondary efficacy endpoints include PFS, TTR, CRR, DoR and OS. The primary efficacy population will include all evaluable subjects who receive at least one dose of study treatment, have measurable disease at baseline per RECIST v1.1, and have at least one post-baseline scan or discontinue study treatment as a result of progressive disease, death, or a treatment-related adverse event before the first post-baseline scan.

Hypotheses testing of ORR will be conducted among evaluable subjects at the dose which meets the safety criterion in Stage 1. Among the 12 evaluable subjects in Stage 1, at least 1 objective response in melanoma subjects would be needed to proceed to Stage 2 for melanoma; and at least 1 objective response in TNBC subjects would be needed to proceed to Stage 2 for TNBC. If there are at least 4 objective responses among the total of 29 evaluable subjects with melanoma and/or at least 5 objective responses among the total of 41 evaluable subjects with TNBC, the null hypothesis will be rejected for melanoma and/or TNBC and the study will be declared a success.

The point estimate along with the exact 95% confidence interval will be computed for ORR and CRR. PFS and OS will be summarized descriptively and graphically using the Kaplan-Meier method. The Kaplan-Meier estimate for the median, first, and third quartiles will be determined along with 95% confidence intervals (CIs). The Brookmeyer-Crowley method will be used for the CI calculations. For the subset of subjects who have a CR or PR, TTR and DoR will be summarized similarly using the Kaplan-Meier method. The Kaplan-Meier

estimate of PFS rate at the landmark times of 6 months and 1 year, and the OS rates at the landmark time of 1 year will be calculated.

Exploratory analyses may be conducted using iRECIST.

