6 ANALYSIS POPULATIONS

The **ABA pre-screening** population will comprise all subjects who have been pre-screened for ABA test only (who have signed the ABA informed consent form but not the full informed consent form).

The **Screening** population will comprise all subjects who have been screened for the study (who have signed the full informed consent form).

The **All Treated** population will comprise all subjects in the Screening population who receive at least one dose of study treatment. The All Treated population will be the primary population for the baseline characteristics and safety analysis and the secondary population for the efficacy analysis.

The **Evaluable** population will comprise all subjects in the All Treated population who 1) have measurable disease at baseline per RECIST 1.1, AND 2) have at least one post-baseline radiological disease assessment, or discontinue study treatment as a result of progressive disease, death, or a treatment-related adverse event before the first post-baseline radiological disease assessment. The Evaluable population will be the primary population for the efficacy analysis.

The **Per-Protocol** population will comprise all subjects in the All Treated population who do not have any important protocol deviations (IPD) as defined in the study IPD list. The Per- Protocol population will be the tertiary population for the efficacy analysis.

In the Screening population, subjects who do not meet eligibility criteria will be defined as screen failures, and subjects who meet all eligibility criteria but do not receive any study treatment will be defined as non-treated subjects. The Screening population will comprise of All Treated subjects, non-treated subjects, and screen failure subjects.

Limited data will be collected for the ABA pre-screening population and the non-treated subjects and screen failure subjects in the Screening population. Summaries of these data may be produced:

- ABA Pre-screening population: ABA level at screening, demography, inclusion/exclusion, adverse event (if any), concomitant medication (if any) and death data will be collected;
- Screen failure subjects: ABA level at screening, demography, inclusion/exclusion, adverse event (if any), concomitant medication (if any) and death data will be collected;

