11 EFFICACY ANALYSIS

The primary efficacy population will be the Evaluable population, the secondary efficacy populations will be the All Treated, and the tertiary efficacy population will be the PP population.

Efficacy data will be summarized separately for each tumor type. Listings of efficacy data will include both tumor types. Unless stated otherwise, all listings in this section will be produced using the All Treated population.

The definition efficacy endpoints are based on US Food and Drug Administration Guidance for Industry: Clinical Trial Endpoints for the Approval of Cancer Drugs and Biologics, May 2007.

The list of displays for efficacy analysis is shown in Section 15.2.

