11.2.5 Overall Survival

The overall survival is defined as the time from the date of the first dose until the date of death due to any causes. For subjects who have not died or who are lost to follow-up or withdraw consent, OS will be censored at the date of the last contact.

The overall survival will be summarized descriptively using the Kaplan-Meier method for the Evaluable, All Treated and PP populations. The Kaplan-Meier estimate for the median, first and third quartiles will be determined along with 95% confidence intervals (CI). The Brookmeyer-Crowley method will be used for the confidence interval calculation. The Kaplan-Meier estimate of OS rate at landmark times including but not limited to 3, 6, 9, 12, 18, and 24 months will be summarized. The overall survival will also be summarized by status of post study treatment new anti-cancer therapy (Yes or No) for the All Treated population. The Kaplan-Meier Plot of OS will be provided for the Evaluable and All Treated population. Listing of OS will be provided using the All Treated population.

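### The lead overall survival estimate is taken from the scan-based Evaluable population, although survival needs no scan and is followed in all treated subjects

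*Protocol*

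**What the plan says.** The objective in Protocol 3.2 concerns subjects treated with the combination: "To measure overall survival (OS) and OS rate at 1 year in subjects with advanced melanoma or metastatic TNBC when treated with Imprime PGG". Protocol 9.1.3 classes OS with the efficacy endpoints: "the secondary efficacy endpoints include PFS, TTR, CRR, DoR and OS". SAP 11.2.5 counts OS from first dose to death from any cause.

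The population rule covers all efficacy endpoints. SAP 11 states: "The primary efficacy population will be the Evaluable population, the secondary efficacy populations will be the All Treated", with Per-Protocol third. Protocol 9.1.3 limits the primary efficacy population to dosed subjects who "have measurable disease at baseline per RECIST v1.1, and have at least one post-baseline scan". SAP 6 also admits unscanned subjects who "discontinue study treatment as a result of progressive disease, death, or a treatment-related adverse event before the first post-baseline radiological disease assessment". Neither document makes an exception for OS.

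SAP 11.2.5 lists three OS populations without re-ranking them: "The overall survival will be summarized descriptively using the Kaplan-Meier method for the Evaluable, All Treated and PP populations". It also plans Kaplan-Meier plots for Evaluable and All Treated, and an All Treated listing.

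Follow-up does not stop with treatment. Protocol 5.8.1 says of subjects who stop study drug: "The subject will continue to be followed for survival for the duration of the study". The exception is withdrawal of consent for that follow-up. Protocol 7.4.3 and Appendix 14.6 also call for continued imaging every 6 weeks in subjects who stop without documented progression.

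**The concern.** The scan condition suits ORR, because response cannot be assessed without imaging. OS needs only a first dose and a date of death or last contact. Applying the scan condition to OS lets events after Day 1 decide who counts in a time-to-death analysis that starts on Day 1.

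The subjects at issue stop before any post-baseline scan because of an unrelated adverse event, intercurrent illness, their own decision or noncompliance, and are not imaged later. Part of the sorting rests on causality. Under Protocol 8.1.2 an event is related only if no other cause can be identified, so an early exit with a plausible alternative cause can put the subject outside the Evaluable set. Protocol 5.9 allows such subjects to be replaced, which restores the evaluable count and makes the omission less visible.

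At stake is the lead OS curve, its median and the 1-year rate. If the omitted subjects die earlier than the rest, these figures look better than survival in the treated subjects named in the objective.

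**Working it through.** **The plan's own figures.** The documents give no planned value for OS. The ORR design figures do reproduce. An exact two-stage binomial calculation (continue on at least 1 response in 12) gives type I error 0.0500 and power 0.902 for at least 4 of 29 in melanoma. It gives 0.0452 and 0.906 for at least 5 of 41 in TNBC. Early termination under the null is 0.95^12 = 0.540. These agree with the stated 0.05, 90% and 0.54. OS plays no part in them.

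**Who is left out.**

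| Course of a treated subject | In Evaluable | Survival followed |
|---|---|---|
| Measurable disease, any post-baseline scan, on or off treatment | Yes | Yes |
| Measurable disease, no scan, stopped for progression, death or related adverse event | Yes | Yes |
| No scan, stopped for another reason | No | Yes, unless lost or consent withdrawn |
| No measurable disease at baseline | No | Yes, unless lost or consent withdrawn |

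The last row should be nearly empty, because measurable disease is inclusion criterion 7. The third row is the point.

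**Inputs for the size.**
- N = 41 evaluable TNBC subjects and 29 melanoma subjects (Protocol 9.1.3).
- Median OS 8.9 months, 95% CI 7.2 to 11.2, from the pembrolizumab monotherapy study in previously treated TNBC (Protocol 4.3.1). It is used here as an assumed evaluable median with exponential survival.
- k = number omitted. The documents do not give it; 1 to 5 is assumed. They are taken as additional to N because Protocol 5.9 allows replacement.
- s = 1-year survival of the omitted subjects. The documents do not give it; 0, half the evaluable rate and 1 are shown.

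**Formulas.** Evaluable 1-year rate S = 2^(-12/8.9) = 0.3928. All Treated rate = (N·S + k·s)/(N + k). Evaluable minus All Treated = [k/(N + k)]·(S − s). The sign is the sign of S − s.

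**Results for TNBC, N = 41, Evaluable rate 39.28%.**

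| k | All Treated, all omitted dead by 1 year | Difference, s = 0 | Difference, s = S/2 | Difference, s = 1 |
|---|---|---|---|---|
| 1 | 38.34% | +0.94 | +0.47 | −1.45 |
| 2 | 37.45% | +1.83 | +0.91 | −2.82 |
| 3 | 36.60% | +2.68 | +1.34 | −4.14 |
| 4 | 35.78% | +3.49 | +1.75 | −5.40 |
| 5 | 35.01% | +4.27 | +2.13 | −6.60 |

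Differences are in percentage points. Example: k = 5, s = 0 gives 41 × 0.3928 / 46 = 0.3501.

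**Sensitivity.** With medians of 7.2 and 11.2 months, S is 31.5% and 47.6%, and the all-dead difference for k = 1 to 5 runs from 0.8 to 3.4 and from 1.1 to 5.2 points. For melanoma the documents give no OS benchmark. If the same three medians are assumed with N = 29, the all-dead difference runs from 1.1 to 7.0 points.

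**Scale.** With 41 subjects and no censoring before 1 year, the approximate 95% half-width at 39.3% is 1.96 × √(0.393 × 0.607 / 41) = 0.15, or 15 points.

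**The case against.** The case for leaving the plan alone is substantial. Unscanned subjects who stop for progression, death or a treatment-related adverse event are already Evaluable, and SAP 9.1.2 treats missing relatedness as related. As worded, the Evaluable definition does not require the scan to be on treatment. The off-treatment imaging in Protocol 7.4.3 and Appendix 14.6 therefore brings many other early leavers back in. Some of those who remain outside will be lost or will have withdrawn consent, and for them All Treated adds only a short censored time. SAP 11.2.5 already plans OS in All Treated with median, quartiles, landmark rates, plot and listing. SAP 12.5 summarises all deaths, and SAP 10.1 lists subjects excluded from Evaluable. OS is descriptive, and the likely shift is small beside a 15-point half-width.

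All of that stands. It narrows the group and limits the consequence, but it does not justify the ranking. A selection effect is not reflected in the confidence interval, and the output that avoids it is placed second.

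A reader might also take the exclusion rate from the sponsor's earlier lung cancer trials. LCA0822 reported "36.6% in the Imprime PGG arm vs. 23.1% in the Control arm" by central read. If Fisher's test was used, 15/41 against 6/26 gives the reported p = 0.2895. The investigator read fits 22/46 against 6/26 (p = 0.0468), and LCA0821 fits 29/48 against 10/23 (p = 0.2096). Of 59 treated on Imprime PGG, 18, 13 and 11 (31%, 22%, 19%) would then be outside the ORR denominator. Those shares cannot be carried over. They are ORR denominators from first-line chemotherapy trials whose evaluability rules may differ, and in LCA0822 the denominator changes with who read the scans. A 19% share with an assumed median of 2 to 4 months in the omitted subjects would give 5.1 to 7.2 points, but neither input comes from this trial.

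**Conclusion.** The point holds in a limited form. By a blanket rule, the primary OS estimate uses a population whose membership depends on events after Day 1 that OS does not need. It omits treated subjects who left for other reasons and were never scanned, even where their survival is known.

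Two stronger readings are tempting and are not supported. The first is that deaths before a first scan are dropped in general. They are not, because the listed exits, death included, stay in the Evaluable set. The second is that the 1-year OS rate is biased upward. That is plausible if early leavers do worse, but the documents give neither the number nor the survival of the omitted subjects. The difference is zero at equal survival and reverses if they live longer.

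For TNBC, with 1 to 5 omitted subjects all dead by 1 year and exponential survival with median 8.9 months in 41 evaluable subjects, the Evaluable rate is about 1 to 4 points too high. That is the upper end for each number omitted. No hypothesis test or stopping rule uses OS, so the ORR decision is unaffected.

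**What to change.** In SAP 6, 11 and 11.2.5 and in Protocol 9.1.3, name All Treated as the primary population for OS and the 1-year OS rate. Keep the Evaluable and Per-Protocol OS summaries as supportive. The populations for ORR and the other efficacy endpoints need no change on this account.

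The cost is wording only, because the All Treated OS summary, plot and listing are already planned. No new data, subjects or analyses are needed. The headline OS may come out slightly less favourable.
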